 - Those with biopsy results that are positive for a high grade pre-cancerous lesion (CIN 2/3 or CIS) and if the lesion is amenable to cryotherapy or LEEP as per Kenyan national guidelines, will be eligible for randomization. If they are willing to undergo informed consent for the treatment study, they will be randomized to receive either cryotherapy or LEEP (see Study Flow II). Those who decline to participate in the treatment study will be exited and referred to KNH for treatment. Randomization questionnaire will also be completed during this visit.
 - Those patients who do not have lesions which are amenable to cryotherapy due to size or access will not be randomized but will be offered free LEEP and followed up every 6 months for 2 years, the same way as randomized participants. Those who have lesions that are neither amenable to LEEP nor cryotherapy due to size or severity of disease, or anatomy does not allow proper access to the cervix, will be referred to KNH for subsidized care at this government hospital. The study will not pay for this treatment. Patients will be given follow-up appointments in the study clinic after referral to determine outcomes. They will have the option to continue to be followed at the CCSP.

- Those with CIN 1 will not be randomized or exited but will be asked to return to the study clinic after 6 months for a repeat Pap smear.
- Those who show no dysplasia on histology will be exited from the study and referred to the CCSP for further follow-up.
- It is expected that approximately 400 patients will be eligible for randomization. During randomization, a sealed envelope will be opened by the study doctor that will reveal the randomization arm that has been assigned to the study ID number. Randomization assignment will be performed on a computer by [name], the study statistician, in Seattle, and preparation of the envelopes will be performed by the study data manager in Nairobi in conjunction with [name]. This is the standard used for all randomized clinical trials conducted by the University of Washington in Kenya. Study investigators and the study doctor will not have access to the randomization sequence. Study investigators and staff will not be blinded to randomization.
- Those eligible for randomization will have an HIV cervical viral level swab taken before treatment (LEEP or cryotherapy).

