- After receiving LEEP or cryotherapy, women will be given free condoms and advised to abstain from sexual activities for at least 4 weeks. Women will also be offered an information sheet on the treatment procedure and abstinence information to take home for their spouse or partner. Information includes treatment given, recommended abstinence period and reasons for abstaining from sexual intercourse. These information sheets will be optional to maintain patient confidentiality and safety, especially for people who have not disclosed their status.
- Patients undergoing randomization will have the following performed:

- Blood (10mls) will be drawn to check for HIV viral load and CD4 count
 - Cervix will be swabbed to assess the presence of Human Papillomavirus (HPV) prior to LEEP or cryotherapy
 - Cervix will be swabbed for HIV viral level prior to LEEP or cryotherapy
 - LEEP or cryotherapy performed based on randomization envelope
 - Those undergoing LEEP will have the LEEP piece taken for histology
 - “Randomization” questionnaire completed
 - “Treatment” questionnaire completed
4. First, second, and third-week visits for cervical HIV-1 SHEDDING after treatment (~400 patients) (see Study Flow II)
- Patients who have been randomized and received treatment (approximately 400 patients) will be followed every 1 week for 3 weeks AFTER the treatment intervention to assess healing and measure HIV-1 viral shedding from the cervix. These events can be called the 7-9, 8-10, and 9-11-week visit time points and will probably coincide with the eighth, ninth, and tenth week after enrollment. However, for purposes of measuring HIV viral shedding, it is most important that these time points occur 1, 2, and 3 weeks after the treatment intervention. These terms are consistent and are used for descriptive purposes. They will return 3 times over a 3-week interval and have the following performed:
 - Blood (10mls) will be drawn to check for HIV viral load
 - Cervix will be swabbed to assess the presence of HIV-1
 - “Shedding” questionnaire completed

Shedding information will be considered valid if it is obtained \pm 3 days of the scheduled visit. We will collect shedding information for the first three weeks after treatment but if a patient misses those visits but comes back within six weeks, we will still collect the samples just for comparison purposes.

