The sample size was calculated to detect a 10% difference in treatment outcomes between LEEP and cryotherapy (4% versus 14%)²⁶ with 80% power and a 0.05 significance level. Accounting for the possibility of a 20% loss-to-follow-up rate over two years, we estimated that 400 women with high grade lesions would need to be enrolled in the study with 200 women randomized to each arm. It is estimated that 200 women in each arm will allow detection of a 0.25 log₁₀ HIV virus level difference in cervical shedding between the two arms with greater than 90% power. Based on results from an ongoing cervical cancer screening study implemented at the Hope Center in 2009, our estimation of the prevalence of high-grade intraepithelial lesions is about 18%. Given this estimate and the number of women who are likely to be eligible for randomization, we calculate that we need to enroll 2,400 women for initial screening.

The primary analysis of the study will be to compare treatment outcomes between the LEEP and cryotherapy intervention arms in an intent-to-treat analysis. Treatment outcomes will be measured by Pap smears taken every 6 months during two-year follow-up. Pap smears demonstrating high-grade intraepithelial lesions will be considered positive and compared against negative or low-grade intraepithelial lesions. A Chi-square test will be used to compare the percentage of positive Pap smears between the intervention arms at 6, 12, 18, and 24 months. Secondary analyses will compare cervical HIV-1 RNA viral shedding between the treatment arms. A comparison of the average area under the curve (AAUCMB) of long-transformed HIV-1 RNA cervical viral loads will be performed between the two arms using an analysis of covariance (ANCOVA) model.

Our analysis will include contraceptive history as a potential confounder. While there has been some suggestion in the literature that HIV infectivity among women on oral

contraceptives is increased,^{33, 34} a recent study from the UW did not show a significant increase in levels of HIV RNA in cervical samples obtained from women on hormonal contraception.³⁵ A more recent multicenter randomized controlled trial performed in Asia and Africa also did not find an association between hormonal contraceptive use and increased HIV transmission.³⁶ However, increased viral shedding due to hormonal contraceptive use remains an important and interesting question and one that we will examine in our study.

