- Study doctor will collect cervical biopsy specimen under colposcopy and perform endocervical curettage when necessary
- Study nurse or lab assistant will collect blood specimens
- Specimens will be gathered in the laboratory before transfer
- Lab assistant or technologist will record details in lab book. Information includes:
 - Specimen Study ID
 - Date
 - Visit type
 - Time sample was collected
- Pap smear, cervical biopsy, and endocervical curettage specimens will be placed in a cool box and transported to the designated laboratory before 4 pm by the lab assistant or technologist. Designated laboratory will record reception of samples in a book including: specimen study ID, date, time, and number of specimens. Results will be filled in the relevant “Histology Report” and “Cytology Report”.
- One set of blood samples will be sent to the Coptic Hospital for CD4 count. These results will be filled in the “CD4 Report”.
- One set of blood samples will be centrifuged at the study laboratory by the lab technologist located at the Hope Center and frozen in a -80oC freezer for storage. Shipment of samples for analysis of viral levels will be performed on these samples.
- Cervical swabs for HIV will be prepared in the study laboratory and frozen in a -80oC freezer for storage. Cervical swabs for HPV will be stored in storage medium

(preservCyt) at $<25^{\circ}$ C. Shipment of samples for viral analysis will be performed on these samples.

Pap smear and cervical tissue biopsy

- Papanicolaou test: after the application of a speculum, a cervex brush will be inserted to its full length into the endocervical canal so that the shorter outer brush hairs are in contact with the ectocervix. The cervex brush will then be gently pushed whilst being turned 5 times in an anticlockwise direction (2.5 complete turns), in order to collect cells from both the endo- and ecto-cervix. Care will be taken not to touch the tip of the brush in order to avoid cross-contamination. Using the brush, a Pap smear will then be prepared by smearing the brush on a clean glass slide and fixing immediately with 95% isopropyl alcohol for at least 30 minutes at the study clinic. The slide will then be transported to the laboratory to be stained, and the cytology will be reported by a study pathologist from Aga Khan University Hospital using the Bethesda classification.

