- Samples from the colposcopy-directed biopsy of the cervix, endocervical curettage specimen and the LEEP specimen will be fixed in 10% buffered formaldehyde solution and transported for haematoxylin-eosin staining. The histopathology results will be read by a study pathologist from Aga Khan University Hospital, and the biopsy samples will subsequently be preserved and fixed in paraffin. Biopsy blocks will be collected and may be sent to the IARC for further analysis.

Cervical swabs for HIV and HPV

- Dacron swabs will be used to collect samples for HIV from the cervix. Endocervical secretions will be collected by rotating the swab 360 degrees in the outer part of the endocervix.
- For HIV-1 DNA testing, the dry swab will be stored as such in the -80°C freezer.

- For HIV RNA testing, the swabs will be collected in a cryovial containing 1 ml of freezing media and then stored at -80°C.
- Cervical samples for HPV will be taken using cervex brush. The brush will be inserted to its full length into the endocervical canal so that the shorter outer brush hairs are in contact with the ectocervix. The cervex brush will then be gently pushed whilst being turned 5 times (2.5 complete turns), in order to collect cells from both the endo- and ectocervix. Care will be taken not to touch the tip of the brush in order to avoid cross-contamination. The brush containing cervical cellular material will be placed in a vial containing PreservCyt media (Cytoc Corporation) and labeled with the subject identification number of the participant. The brush will be fully rinsed in the media by pressing 10 times against the bottom of the vial, forcing the brush hairs to separate. Finally the brush will be vigorously shaken in the media to remove any residual cells. The brush will NOT be left in the vial, but discarded. It is very important to close the vial very tightly to avoid possible leakage during transport. Cell samples will be stored at the Hope Center at 25°C, and then later transported to the US or to IARC in Europe.

Shipping

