This study will employ interim analyses to assess accumulating study data for early evidence of treatment efficacy. The primary outcome, recurrence of cervical intraepithelial neoplasia grade 2 or 3, will be compared between groups at the following approximate times: months 9, 15, 21 and 27, and for DSMB safety, upon cumulative enrollment and intervention of 100 patients. The decision criteria for stopping the study at each interim analysis are based on O'Brien-Fleming superiority boundary with Type I error controlled at alpha-level $\alpha = 0.05$. In the event that interim analyses are conducted at times other than the preplanned times (e.g. unequal information accrual) the stopping criteria will be adjusted to maintain overall type I error rate of $\alpha = 0.05$. We will use Lan-DeMets alpha spending approach, to make the necessary adjustments. The decision criteria for stoppage are based on a power of 80% to detect a treatment group difference at the end of study.

Report

A formal report prepared by an assigned administrator will be reviewed and approved by the DSMB chair, who will prepare a summary. The minutes and summary will be sent to the full DSMB within three weeks of the meeting. Once approved by the DSMB, the chair of the DSMB will sign on behalf of the board and the report will be forwarded to the participating institutions within 4 weeks of each meeting. The PIs will submit the results of these meetings to the UW Institutional Review Board (IRB), the KNH Ethics Review Committee (ERC), and the Centers for Disease Control (CDC) which is the study sponsor. Each report will conclude with a recommendation to continue or to terminate the study. This recommendation will be made by formal majority vote. A termination recommendation may be made by the DSMB at any time by majority vote. The report will not include un-blinded data or any discussion of the un-blinded data.

Any new findings discovered by the DSMB during the course of the study that may affect the willingness of subjects to remain in the study will be shared by the study doctor or nurse through direct discussions and printed pamphlets.

Sponsor Monitoring

As the study sponsor, the Centers for Disease Control (CDC) may conduct monitoring or auditing of study activities to ensure the scientific integrity of the study and to ensure the rights and protection of study participants. Monitoring and auditing activities may be conducted by:

- CDC staff (“internal”)

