7a. Reasons for being Exited from the program (tick all that apply)

Client has not returned to clinic for 1 year

Poor Adherence

Poor Clinic Attendance

Not willing to disclose HIV status

Referred else where

Tested Negative

Other (specify)

Unknown

8. Has the patient asked to be Unenrolled from the study? Yes No (*If Yes go to 8a, If No go to 9*)

8a. Reasons patient is asking to Unenroll from the study (tick all that apply)

Not willing to attend

Waiting time too long

Conflict with work

Financial problems

Unwilling to attend because of health problems

Family Problems

Client will go to a faith healer

Not willing to disclose HIV status

Referred else where

Other (specify)

Unknown

9. At what point was the patient exited? After Pap smear After Biopsy Mortality Withdrawn from study Other (If other specify)

10. Comment

9. Any microbiological findings? Yes No
 If “Yes”, specify findings:

- Lactobacilli
- Mixed flora
- Bacterial vaginosis
- Candida
- Trichomonas vaginalis
- Actinomyces
- Schistosoma
- Herpes simplex
- Other, specify.....

10. Any reactive changes observed? Yes No
 If “Yes”, specify findings

- Metaplasia
- Inflammatory changes
- Follicular cervicitis
- Parakeratosis
- Atrophy
- Other reactive changes
- If “Yes”, specify.....

11. Squamous epithelium: Normal Abnormal
 If “Yes”, specify findings

- ASC-US Yes No
- ASC-H Yes No
- Low grade SIL Yes No
- With koilocytosis Yes No

- High grade SIL Yes No
- HSIL invasion not ruled out Yes No
- Squamous cell carcinoma Yes No
- Others, specify _____

12. Glandular epithelium: Normal
abnormal

If “Yes”, specify findings

- Abnormal presence of endometrial cells Yes No
- Atypical glandular cells, pref. neoplastic Yes No
- Adenocarcinoma in situ Yes No
- Adenocarcinoma Yes No
 - Endometrial Yes No
 - Endocervical Yes No

Others, specify _____

13. Other

remarks.....

Interviewer number of pathologist

Date: _____

COLPOSCOPIC BIOPSY HISTOLOGY REPORT

First read Re-read 1 Consensus reading Tie-break

Study ID Number _____

Hope ID Number _____

Test/ Visit code _____

Visit (tick one) Initial Visit Month 6 FU Month 12 FU Month 18 FU
 Month 24 FU Other, specify

Interviewer number --- ---- Patient Age _____

1. Date sample was collected in clinic (day/month/year) ____/____/____
2. Time sample was collected in clinic
3. Date sample was received in laboratory (day/month/year) ____/____/____
4. Time sample was received in laboratory

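### No supplied text masks the readers of the primary outcome to arm, and a shared study ID would let a reader infer the arm from the initial LEEP specimen

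*Combined protocol and SAP*

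**What the plan says.** **Blinding.** Study Procedures, section 3 (randomization visit), after describing the envelopes, says: "Study investigators and staff will not be blinded to randomization". It makes no exception for endpoint readers. The masking that the protocol does describe is for the data presented to the DSMB (Confidentiality, in the Data Safety and Monitoring Plan).

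**Primary outcome.** Statistical Methods says "Treatment outcomes will be measured by Pap smears taken every 6 months during two-year follow-up" and "Pap smears demonstrating high-grade intraepithelial lesions will be considered positive and compared against negative or low-grade intraepithelial lesions". Interim Efficacy Analyses words it differently: "The primary outcome, recurrence of cervical intraepithelial neoplasia grade 2 or 3, will be compared between groups". Either way, the outcome is a pathologist's grade.

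**Readers.** Under Laboratory Procedures, for smears: "the cytology will be reported by a study pathologist from Aga Khan University Hospital using the Bethesda classification". For colposcopic biopsies, curettage and LEEP tissue: "The histopathology results will be read by a study pathologist from Aga Khan University Hospital".

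**Specimens and identifiers.** At randomization, "Those undergoing LEEP will have the LEEP piece taken for histology". One study number serves all visits (Ethics, section E), and the receiving laboratory logs specimens by study ID (Laboratory Procedures, Sample collection). The LEEP Biopsy Histology Report carries the study ID and also serves as the laboratory request form (Data Management, Entry). The Cytology Report ends with a field for "Interviewer number of pathologist".

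**Reading system.** The protocol mentions QC re-readings and a consensus result, and the histology forms have boxes for first read, re-read, consensus and tie-break. A QA/QC document is said to be attached as an addendum. Its text is not among the documents supplied.

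**The concern.** High-grade against low-grade or negative is a judgement, and borderline slides can go either way. The protocol's stated hypothesis is that LEEP is better at preventing recurrence. If a reader knows or can work out the arm, expectation can move borderline calls in one arm relative to the other. The chi-square comparison cannot tell such a shift from a treatment effect.

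The clinician who performs the procedure cannot be masked. The person at the microscope can be, so this source of bias is avoidable in an otherwise open trial. The result is meant to inform PEPFAR policy.

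**Working it through.** **1. Can the arm be traced at the laboratory?**

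- Among randomized women, LEEP yields tissue at initial treatment and cryotherapy does not.
- That tissue and the follow-up smears are both read by study pathologists from one hospital.
- Both are logged under the same study ID.

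A follow-up smear can therefore be matched to the presence or absence of an initial LEEP specimen. The link requires a look-up. No passage says that readers do this, and none prevents it.

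**2. Do the re-reads remove the problem?** Re-reading, consensus and tie-break reduce random error. They do not remove an expectation shared by the readers unless the re-readers are masked, and the supplied text does not say that they are.

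**3. How large could the effect be?** The plan gives no figure for reading error, so this is an illustration on assumed shifts.

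Inputs:
- Evaluable women per arm: 200 × (1 − 0.20) = 160, from the planned 200 per arm and 20% loss (Statistical Methods).
- True risk in both arms: (4% + 14%) / 2 = 9%, the midpoint of the design rates.
- Test: Pearson chi-square at 0.05, taken as two-sided because the plan does not state the sidedness.
- Statistic: |z| = |x₁ − x₂|/160 ÷ √[2p̄(1 − p̄)/160], with p̄ = (x₁ + x₂)/320, significant if |z| > 1.96. The false-positive rate is the exact sum of binomial probabilities over all significant pairs (x₁, x₂).

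*Model A: shift split equally* (one arm read down by half, the other up by half).

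| Shift | Observed risks | False-positive rate |
|---|---|---|
| 0 | 9.0% v 9.0% | 5.0% |
| 2 points | 8.0% v 10.0% | 9.6% |
| 3 points | 7.5% v 10.5% | 15.5% |
| 5 points | 6.5% v 11.5% | 34.8% |

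*Model B: over-calling in the cryotherapy arm only.* A share s of true negatives is called positive, so the observed risk is 0.09 + s × 0.91.

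| s | Observed risks | False-positive rate |
|---|---|---|
| 1% | 9.0% v 9.9% | 5.9% |
| 2% | 9.0% v 10.8% | 8.5% |
| 3% | 9.0% v 11.7% | 12.7% |
| 5% | 9.0% v 13.6% | 25.3% |

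Across the two models, a difference of about 2 to 3 points gives 8.5% to 15.5%, or roughly 9-16%.

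*Sensitivity to the true risk.* At 4%, a 2- or 3-point shift gives 14% or 27% under Model A and 12% or 20% under Model B. At 14%, the figures are 8% or 12% and 7% or 10%.

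*The opposite direction.* If readers missed a quarter of true cryotherapy positives, 14% would be read as 14% × 0.75 = 10.5%. Power against 4% would fall from 88% to 61%.

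**The case against.** The strongest reply is that the plan is silent about readers rather than against masking them. The blinding sentence closes a passage about envelopes and access to the sequence at the clinic. The Personnel section has no pathologist role; pathologists appear there only as the people who receive specimens and return results. A reader might infer that the protocol declares the pathologists unblinded. The documents do not support that: it would rest on the word study in their title and a numeric code on a form. The addendum may already require masked reading. This part of the reply stands, and it is why checking the addendum comes first.

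A reader might also infer that any LEEP record reveals the LEEP arm. It does not. Non-randomized women whose lesions are not amenable to cryotherapy have LEEP, as may women with three consecutive CIN 1 results, and women in either arm with a treatable recurrence. The link holds only for randomized women and only for the specimen from initial treatment.

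Nor do the documents show that one person reads both specimen types. What they share is the readers' hospital; specimens go to a designated laboratory, and another passage sends the laboratory forms to a differently named one. The top of the Cytology Report form is missing from the extracted text, so a Hope ID on smears cannot be confirmed. The link rests on the study ID alone.

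Finally, every shift is assumed. The 5-point case, 6.5% against 11.5%, is a 1.77-fold difference in reading and is not small. A 1% one-sided over-call barely matters (5.9%).

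These points narrow the concern but do not remove it. No supplied text masks the readers, and the arm can be inferred.

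**Conclusion.** The point holds as an unaddressed risk of bias in a subjective primary endpoint that is cheap to close. The documents do not show that readers are told the arm, or that any bias occurred. On the assumptions of 160 evaluable women per arm, 9% true risk in both and a two-sided test, a reading difference of about 2 to 3 points would raise the false-positive rate from 5% to about 9-16%. The range depends on whether the difference comes from one arm or is split between both. The conclusion depends on the missing addendum: if it masks all readers and separates the specimen codes, only the wording of the blinding sentence is left to correct.

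**What to change.** 1. Check the QA/QC addendum for masking of cytology and histology readers. If it is there, cross-refer to it in the randomization visit section and qualify the blinding sentence so that the two do not conflict.
2. If it is not, amend that sentence: clinic staff and investigators are unmasked, but every cytology and histology reader (first read, re-read, consensus and tie-break) is masked to arm.
3. Send follow-up smears and biopsies under a laboratory code that cannot be linked to the initial LEEP specimen, keep treatment off the request form, and hold the key to the codes in the data office.

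**Cost.** Protocol wording, plus one relabelling and one re-linkage step; no new reader, visit or procedure. The re-linkage is a real addition to the results pathway, because cytology and histology results drive recall and tracing. It must be set up so that it does not delay the return of those results.
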